3.2 DISCUSSION OF TRIAL DESIGN, INCLUDING THE CHOICE OF CONTROL GROUP(S)

This trial is a single-arm trial with multiple dose cohorts and there is no control group. This is a standard design in Phase I trials in Oncology clinical trials where the assessment of MTD, safety and PK are the main objectives.

A Bayesian Logistic Regression Model (BLRM) will be used to guide the dose-finding, in order to escalate the dose into a dose range where efficacy or target engagement may be seen while still minimizing the risk of undue toxicity.

A SMC will be established to ensure the patient safety (for details, see section [8.7](#)). The SMC will monitor the safety data on an ongoing basis, interpret the DLT risk estimate provided by BLRM, and make decisions regarding the dose level to be investigated, the MTD and/or RD, and the necessity of trial plan modifications in case of emerging safety issues.

3.3 SELECTION OF TRIAL POPULATION

A log of all patients enrolled into the trial (i.e. who have signed informed consent) will be maintained in the Investigator Site File (ISF) irrespective of whether they have been treated with investigational drug or not.

If a patient is enrolled in error (does not meet all inclusion criteria or meets one or more exclusion criteria on the day of enrolment), the sponsor should be contacted immediately.

Approximately 21 patients (12 in Part A, 9 in Part B) are planned to be included. This trial will be conducted in Japan and Taiwan. Japanese patients will be recruited in all treatment cohorts, and Taiwanese patients will be recruited in the highest planned dose in Part A and all cohorts in Part B (for details, please refer to section [4.1.3](#)). This design provides the

safety/PK data in Japanese patients in multiple dose levels, and also gives the safety/PK data in Taiwanese patients.

3.3.1 Main diagnosis for trial entry

Patients with a confirmed diagnosis of advanced, unresectable and/or metastatic solid tumours, who have failed standard treatment, or for whom no therapy of proven efficacy exists, or who are not amenable to standard therapies.

Please refer to section [8.3.1](#) (Source Documents) for the documentation requirements pertaining to the in- and exclusion criteria.

The grade of adverse events mentioned in this protocol is based on Common terminology criteria for adverse events (CTCAE) version 5.0 ([R18-1357](#)).

3.3.2 Inclusion criteria

1. Of legal age (according to local legislation) at screening. No upper limit.
2. Signed and dated written informed consent in accordance with International Council on Harmonisation (ICH) Good Clinical Practice (GCP) and local legislation prior to admission to the trial.
3. Male or female patients. Women of childbearing potential (WOCBP)¹ and men able to father a child must be ready and able to use highly effective methods of birth control per ICH M3 (R2) that result in a low failure rate of less than 1% per year when used consistently and correctly, starting with the screening visit and through 6 months after the last dose of study treatment. A list of contraception methods meeting these criteria is provided in the patient information. The requirement of contraception does not apply to women of no childbearing potential and men not able to father a child, but they must have an evidence of such at screening.
4. Eastern Cooperative Oncology Group (ECOG) performance status: 0 to 1
5. Patients with a confirmed diagnosis of advanced, unresectable and/or metastatic solid tumours, who have failed standard treatment, or for whom no therapy of proven efficacy exists, or who are not amenable to standard therapies.
6. Presence of at least one measurable lesion according to RECIST 1.1.
7. Life expectancy of at least 12 weeks after the start of the treatment according to the Investigator's judgement
8. For Part B: Patients must have at least 1 tumour lesion amenable to biopsy, and must be willing to undergo a biopsy prior to first treatment and after 3 weeks while on therapy.
9. For Part B: Patients with following cancer types: bladder, colon, breast, NSCLC, ovarian, pancreatic, renal, esophagogastric, sarcoma, prostate, and melanoma.

¹ A woman is considered of childbearing potential (WOCBP), i.e. fertile, following menarche and until becoming post-menopausal unless permanently sterile.

Permanent sterilisation methods include hysterectomy, bilateral salpingectomy and bilateral oophorectomy.

Tubal ligation is NOT a method of permanent sterilisation.

A postmenopausal state is defined as no menses for 12 months without an alternative medical cause.

3.3.3 Exclusion criteria

1. Major surgeries (major according to the Investigator's assessment) performed within 12 weeks prior to the first administration or planned within 12 months after screening (e.g., hip replacement), or moderate surgeries (moderate according to the Investigator's assessment) performed within 4 weeks prior to the first administration.
2. Presence of active invasive cancers other than the one treated in this trial within 5 years prior to screening, except for appropriately treated basal cell carcinoma of the skin, or *in situ* carcinoma of uterine cervix, or other local tumours considered cured by local treatment
3. Patients who must or wish to continue the intake of restricted medications or any drug considered likely to interfere with the safe conduct of the trial
4. Previous administration of BI 891065 or other SMAC mimetic/IAP inhibitor
5. Patients who have been treated with any other anticancer drug or investigational drug, within 4 weeks or within 5 half-life periods (whichever is shorter) prior to first administration of BI 891065
6. Persistent toxicity from previous treatments that has not resolved to \leq Grade 1 (except for alopecia and Grade 2 neuropathy due to previous treatments)
7. Active, known or suspected autoimmune disease except vitiligo or resolved asthma/atopy
8. (Part B only) Patients removed from previous anti-PD-1 or anti-PD-L1 therapy because of a severe immune-related adverse event (irAE)
9. History (including current) of interstitial lung disease or pneumonitis within 5 years
10. Any of the following cardiac criteria:
 - Mean resting corrected QT interval (QTcF) >480 msec
 - Any clinically important abnormalities (as assessed by the investigator) in rhythm, conduction, or morphology of resting Electrocardiograms (ECGs), e.g., complete left bundle branch block, third degree heart block
 - Any factors that increase the risk of QTc prolongation or risk of arrhythmic events such as heart failure, hypokalaemia, congenital long QT syndrome, family history of long QT syndrome or unexplained sudden death under 40 years-of-age, or any concomitant medication with known or possible risk of QT interval prolongation
 - Patients with an ejection fraction (EF) of either $<50\%$ or less than the lower limit of normal of the institutional standard will be excluded, whichever is lower. Only in cases where the Investigator (or the treating physician or both) suspects cardiac disease with negative effect on the EF, will the EF be measured during screening using an appropriate method according to local standards to confirm eligibility (e.g., echocardiogram [ECHO], multi-gated acquisition scan [MUGA]). A historic measurement of EF no older than 6 months prior to first administration of study drug can be accepted provided that there is clinical evidence that the EF value has not worsened since this measurement in the opinion of the Investigator or of the treating physician or both.
11. Inadequate organ function or bone marrow reserve as demonstrated by the following laboratory values:
 - Absolute neutrophil count (ANC) $<1.5 \times 10^9/L$ ($<1500/\text{mm}^3$)
 - Platelet count $<100 \times 10^9/L$ ($<100,000/\text{mm}^3$)
 - Haemoglobin $<9.0 \text{ g/dL}$

Proprietary confidential information © 2021 Boehringer Ingelheim International GmbH or one or more of its affiliated companies

- Alanine transaminase (ALT) >3 times the upper limit of normal (ULN) if no demonstrable liver lesion(s) (primary or metastases) or >5 times ULN in the presence of liver lesion(s)
- Aspartate aminotransferase (AST) >3 times the ULN if no demonstrable liver lesion(s) or >5 times ULN in the presence of liver lesion(s)
- Total bilirubin >1.5 times ULN, except for patients with Gilbert's syndrome who are excluded if total bilirubin >3.0 times ULN or direct bilirubin >1.5 times ULN
- Serum creatinine > 1.5 x ULN (measured by enzymatic assay, Isotope dilution mass spectroscopy [IDMS] standardised Jaffe assay, or non-IDMS Jaffe assay). If serum creatinine is > 1.5 x ULN, patient is eligible if concurrent estimated glomerular filtration rate (eGFR) is \geq 30 mL/min/1.73m² (measured or calculated by Chronic Kidney Disease Epidemiology [CKD-EPI] formula)

12. Human immunodeficiency virus (HIV) infection. Test results obtained in routine diagnostics are acceptable if done within 6 months before the informed consent date.

13. Any of the following laboratory evidence of hepatitis virus infection.

- Positive results of hepatitis B surface (HBs) antigen
- Presence of hepatitis B core (HBc) antibody together with hepatitis virus B (HBV) Deoxyribonucleic acid (DNA)
- Presence of hepatitis virus C (HCV) antibody together with HCV Ribonucleic acid (RNA)

In Part A, test results obtained in routine clinical practice are acceptable if done within 6 months before the informed consent date.

14. Known relevant hypersensitivity to the trial drugs or their excipients based on the investigator's assessment

15. Serious concomitant disease or medical condition affecting compliance with trial requirements or which are considered relevant for the evaluation of the efficacy or safety of the trial drug, such as cardiac, neurologic, psychiatric, infectious disease or active ulcers (gastro-intestinal tract, skin) or laboratory abnormality that may increase the risk associated with trial participation or trial drug administration, and in the judgment of the Investigator would make the patient inappropriate for entry into the trial.

16. Chronic alcohol or drug abuse or any condition that, in the Investigator's opinion, makes them an unreliable trial patients, unlikely to complete the trial, or unable to comply with the protocol procedures

17. Women who are pregnant, nursing, or who plan to become pregnant during the trial. Women who are nursing can be enrolled if they stop nursing. In this case, the patient cannot resume nursing even after discontinuation of study treatment.

18. Untreated brain metastasis(es) that may be considered active. Patients with previously treated brain metastases may participate provided they are stable (i.e., without evidence of PD by imaging for at least 4 weeks prior to the first dose of trial treatment, and any neurologic symptoms have returned to baseline), and there is no evidence of new or enlarging brain metastases

19. Patients with known leptomeningeal disease

20. Patients receiving systemic treatment with any immunosuppressive medication within 1 week prior to treatment start (steroids of max. 10 mg/day prednisolone equivalent per day are allowed, topical and inhaled steroids are not considered as immunosuppressive).

3.3.4 Withdrawal of patients from treatment or assessments

Patients may discontinue trial treatment or withdraw consent to trial participation as a whole (“withdrawal of consent”) with very different implications; please see sections [3.3.4.1](#) and [3.3.4.2](#) below.

Every effort should be made to keep the patients in the trial: if possible on treatment, or at least to collect important trial data. Measures to control the withdrawal rate include careful patient selection, appropriate explanation of the trial requirements and procedures prior to trial enrolment, as well as the explanation of the consequences of withdrawal.

The decision to discontinue trial treatment or withdraw consent to trial participation and the reason must be documented in the patient files and case report form (CRF). If applicable, consider the requirements for Adverse Event collection reporting (please see sections [5.2.6.2.1](#) and [5.2.6.2](#)).

3.3.4.1 Discontinuation of trial treatment

An individual patient will discontinue trial treatment if:

- The patient wants to discontinue trial treatment, without the need to justify the decision.
- The patient has repeatedly shown to be non-compliant with important trial procedures and, in the opinion of both, the investigator and sponsor representative, is not willing or able to adhere to the trial requirements in the future.
- The patient needs to take concomitant medication that interferes with the investigational medicinal product or trial assessments. Refer to section [4.2.2.1](#) for prohibited concomitant medications.
- Progressive disease according to RECIST v1.1 and/or iRECIST. Refer to section [5.1.1](#) for details and exceptions.
- The patient can no longer receive trial treatment for medical reasons (such as surgery, other diseases, or pregnancy).
- The patient experiences an AE requiring treatment discontinuation as listed in section [4.1.6](#).

Even if the trial treatment is discontinued, the patient remains in the trial and will undergo the procedures for the end of treatment visit and follow-up visits as outlined in the [Flow Chart](#) and section [6.2.3](#).

For all patients the reason for withdrawal from trial treatment (e.g. AEs) must be recorded in the CRF. These data will be included in the trial database and reported.

Patients meeting the following criteria will be considered non-evaluable for DLT. If less than two patients are evaluable for DLT in a cohort, the non-evaluable patients will be replaced;

- Patient withdrawal for a reason other than DLT before completing the first treatment cycle
- Patients who have reduced BI 891065 dose level during the first treatment cycle, unless they develop a DLT

Proprietary confidential information © 2021 Boehringer Ingelheim International GmbH or one or more of its affiliated companies

- Patient who can't be assessed for safety due to missed visits in the first cycle of treatment and who does not experience DLTs
- Patient who misses >5 doses of BI 891065 during the first treatment cycle for reasons other than treatment-related AEs and who does not experience DLTs
- (Part B only) Patients who have received less than 50% of the BI 754091 initial dose, unless they develop a DLT

Patients who miss one visit during the first treatment cycle may be replaced after discussion between the sponsor and the investigator if the information that needs to be collected during this visit is not available and makes the patient non-evaluable for determining DLT. All other patients who withdraw, including all patients who are withdrawn from the trial due to a DLT, and all patients who withdraw after the first treatment cycle, will not be replaced.

If a patient should become pregnant during the trial, the study treatment must be immediately stopped. The patient will be followed up until delivery or termination of pregnancy (see Section [5.2.6.2.3](#) for information on pregnancy forms). The data of the patient will be collected and reported in the electronic case report form (eCRF) until the last patient's last visit and any events occurring thereafter will be reported in the BI drug safety database.

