3. DESCRIPTION OF DESIGN AND TRIAL POPULATION

3.1 OVERALL TRIAL DESIGN AND PLAN

This is a Phase I, open-label, non-randomised, multicentre trial of BI 891065 given as single agent (Part A) and in combination with BI 754091 (Part B). The data obtained from the trial will determine the MTD estimate for each Part based on a Bayesian logistic regression model (BLRM) with overdose control ([R13-4803](#)). The BLMR estimates the MTD by updating estimates of the probability of observing a DLT in the MTD evaluation period for each dose level in the trial as patient information becomes available. At any time in the trial, it will not be permitted to escalate to a dose which does not fulfil the EWOC principle (refer to section [7](#)). Dose-escalation will be restricted to a maximum of 100 % from the previous dose.

In Part A, successive cohorts of patients will receive increasing doses of BI 891065. The starting dose of BI 891065 is 100 mg once daily. The dose escalation continues until the MTD is reached, or the safety in the highest planned dose level (400 mg total daily dose of BI 891065) is confirmed. Depending on the occurrence of DLTs or other relevant safety information, SMC may decide to decrease the dose of BI 891065. For any dose-escalation cohort, at least three patients will be enrolled. SMC may decide enrolment of further patients. However, in the case that only two patients are evaluable (i.e. one patient is not evaluable) and neither has experienced a DLT within the MTD evaluation period, then dose-escalation can occur based on these two patients.

A Safety Monitoring Committee decides the size for the next dose escalation cohort. After all patients in a cohort have either experienced a DLT or have been observed for at least the MTD evaluation period without experiencing a DLT, the BLMR will be updated with the newly accumulated data. The overdose risk will then be calculated for each dose, and escalation will be permitted to all doses which fulfil the EWOC criterion and the additional 100 % escalation rule. Based on the model and on other available information, the members of the SMC will reach a joint decision on the next dose level to be investigated.

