7.3.1 General considerations

7.3.1.1 Patient analysis sets

Treated set (TS):

This patient set includes all patients who were documented to have received at least one dose of any trial medication. The TS is used for safety analyses and in efficacy analyses.

MTD evaluation set:

This patient set includes all patients who were documented to have received at least one dose of any trial medication and were considered evaluable for DLT assessment (see section [3.3.4.1](#)). The MTD evaluation set will be used for the primary analyses of DLTs and MTD determination.

Rules for replacement of patients are defined in the section [3.3.4.1](#). The list of replaced patients will be stored in the trial master file.

Pharmacokinetic parameter analysis set (PKS):

This set includes all patients in the treated set (TS) who provide at least one PK endpoint that was not excluded due to a protocol deviation relevant to the evaluation of PK or due to PK non-evaluability (as specified in the following subsection 'Pharmacokinetics'). Thus, a patients will be included in the PKS, even if he/she contributes only one PK parameter value for one period to the statistical assessment. Descriptive and model based analyses of PK parameters will be based on the PKS.

ECG Set:

This set includes all patients in the treated set who do not have an artificial pacemaker and have at least one on-treatment value for at least one ECG variable.

ECG Pharmacokinetic Concentration Set (ECGPCS):

This set includes all patients from the ECG Set who provide at least one time-matched pair of valid BI 891065 plasma concentration and corresponding ECG variable to be used in the exposure-response analysis.

The decision about concentration value validity needs to be made within the Clinical Pharmacology group.

The analysis of ECG data will be based on the ECG Set, except those analyses concerning the relationship between plasma concentrations and ECG variables which will be based on the ECGPCS. Listings for patients with artificial pacemakers will be based on the TS.

Adherence to the protocol will be assessed by the trial team. Important protocol deviations (IPD) categories will be specified in the IQRMP, IPDs will be identified no later than in the

Report Planning Meeting, and the IPD categories will be updated as needed.

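### The first non-evaluability criterion in protocol 3.3.4.1 does not keep a patient who has a cycle-1 DLT and then leaves cycle 1 for an unrelated reason

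*Protocol*

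**What the plan says.** Protocol 3.3.4.1 opens its list with "Patients meeting the following criteria will be considered non-evaluable for DLT", so meeting any one item is enough. The items are:

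1. "Patient withdrawal for a reason other than DLT before completing the first treatment cycle"
2. "Patients who have reduced BI 891065 dose level during the first treatment cycle, unless they develop a DLT"
3. "Patient who can't be assessed for safety due to missed visits in the first cycle of treatment and who does not experience DLTs"
4. More than five missed doses of BI 891065 in cycle 1, "for reasons other than treatment-related AEs and who does not experience DLTs"
5. Part B only: "Patients who have received less than 50% of the BI 754091 initial dose, unless they develop a DLT"

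Protocol 7.3.1.1 defines the MTD evaluation set by reference to this list and adds: "The MTD evaluation set will be used for the primary analyses of DLTs and MTD determination". Protocol 2.1.2 likewise bases the MTD estimate on patients evaluable under 3.3.4.1. SAP 6.3 repeats the set and its use without adding an exception for patients with a DLT.

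Protocol 3.1 allows escalation from a reduced cohort "in the case that only two patients are evaluable (i.e. one patient is not evaluable) and neither has experienced a DLT" in the evaluation period. The same section has the model updated once every patient in the cohort has either had a DLT or completed the evaluation period without one.

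**The concern.** Items 2 to 5 each ask whether the patient had a DLT. Item 1 asks only why the patient left. Take a patient with a qualifying toxicity on Day 8 who leaves on Day 17 for progression or by choice. Both are listed reasons for stopping treatment in 3.3.4.1. The withdrawal is not due to the DLT, so item 1 applies as written. An observed event is then removed from the primary endpoint and from the data that drive the overdose criterion.

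The loss is one-sided. Removing a patient who had a DLT lowers the estimated toxicity, and in cohorts of about three patients one event carries much of the information.

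**Working it through.** **Can the sequence occur?** Protocol 4.1.6 has non-immune Grade 3 events lead to a pause rather than to withdrawal. Protocol 4.1.7 counts many Grade 3 non-haematological toxicities as DLTs. A patient can therefore have a DLT, remain in the trial, and leave later in the same 21 days for another reason.

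**Model inputs (Part A, q.d. dosing).**
- Model (7.1.1): logit(π_d) = log α + β·log(d/200).
- Prior (Table 7.1.1: 2) on (log α, log β): weight 0.9 on means (−3.66, −0.28), SDs (1.20, 0.83), correlation −0.10; weight 0.1 on means (−3, 0), SDs (2, 1), correlation 0.
- Likelihood: binomial at each dose.
- EWOC (7.1.1): P(π_d ≥ 0.33) must be below 0.25.
- Escalation is capped at 100% of the previous dose.

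The posterior was computed by numerical integration on a grid. P(OD) below means the posterior P(π_d ≥ 0.33).

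**Reproducing the protocol's figures first.**

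| Case | Printed P(OD) | Recomputed |
|---|---|---|
| Prior, 400 mg (Table 7.1.1: 3) | 0.072 | 0.074 |
| Table 10.4.1: 1, scenario 3, at 100 mg | 0.316 | 0.308 |
| Scenario 6, at 200 mg | 0.193 | 0.192 |
| Scenario 7, at 200 mg | 0.140 | 0.144 |
| Scenario 11, at 400 mg | 0.413 | 0.411 |

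All agree within 0.01.

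**Single-DLT cases: the next dose does not change.**
- 1/3 at 100 mg, against 0/2 with the DLT patient dropped: P(OD) at 400 mg is 0.182 against 0.063. The model prefers 400 mg in both and the cap gives 200 mg in both.
- 0/3 at 100 mg, then 1/3 at 200 mg against 0/2: P(OD) at 400 mg is 0.158 against 0.046. The model gives 400 mg in both.

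**Cases where the dropped DLT changes the result.**
- 1/3 at 100 mg (the count that Table 7.1.2: 1 reports for this trial), then a hypothetical 1/3 at 200 mg. P(OD) at 400 mg is 0.303, which fails EWOC. With 0/2 recorded at 200 mg it is 0.103, which passes, and 400 mg has the highest target-interval probability of the doses examined (0.234). The two remaining patients are DLT-free, so the two-patient rule in 3.1 is met, and 200 to 400 mg is exactly a 100% step. Under 3.3.4.1 the dropped patient would not be replaced, because two evaluable patients remain.
- 0/3 at 100 mg, 0/3 at 200 mg, 3/6 at 400 mg (scenario 11). P(OD) at 400 mg is 0.411, which fails. Recorded as 2/5 it is 0.195, which passes.

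**Cases that look similar but do not open escalation by that route.**
- 2/3 at 100 mg recorded as 1/2: P(OD) at 100 mg falls from 0.308 to 0.071.
- 0/3 at 100 mg, then 2/3 at 200 mg recorded as 1/2: P(OD) at 400 mg falls from 0.438 to 0.187.

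In both, one of the two remaining patients has a DLT, so the two-patient rule is not met.

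**Regimen.** These figures are for 400 mg q.d. The protocol models 200 mg b.i.d. as 300 mg q.d. For that regimen in the first decisive case, P(OD) is 0.233 with the DLT kept and 0.067 without it, so it passes EWOC either way.

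**The case against.** The strongest reply is that item 1 has its own carve-out: a patient who withdraws because of the DLT stays evaluable. Many exits after toxicity will be of that kind, since 4.1.7 makes permanent discontinuation under 4.1.6, and a pause of seven days or more for treatment-related events in cycle 1, DLT criteria in their own right. This stands. It narrows the gap to a DLT followed by an independent exit, both inside 21 days.

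The early independent exit may also be rare. The first scheduled imaging is at week 6, clinically stable patients may continue past initial progression (5.1.1), and entry requires ECOG 0 to 1 and a life expectancy of at least 12 weeks. This also stands, although the documents give no frequency either way.

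The intent seems clear from the other four items and from the update rule in 3.1, under which a DLT completes a patient's observation. That is a reason to align item 1 with them. The 3.1 sentence governs when the model is updated and does not redefine the analysis set.

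A reader might infer that the DLT disappears from view. It does not. DLTs are reported to the sponsor within 24 hours, the SMC weighs all available information, and SAP 7.4.1 tabulates treated-set DLTs and runs the model a second time on them. But SAP 7.4.1 specifies that run for the trial report, and protocol 2.1.1 places the all-cycle rerun at the end of escalation, for the RD. Neither enters the cohort-by-cohort EWOC calculation or the MTD estimate.

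A reader might also infer that any dropped DLT opens escalation. The single-DLT and the 2/3-recorded-as-1/2 cases do not support that.

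**Conclusion.** The concern holds as a gap in the wording of one criterion. Taken literally, item 1 removes an observed cycle-1 DLT from the primary DLT count and from the MTD model when the patient later leaves cycle 1 for an unrelated reason. Nothing in protocol 7.3.1.1 or SAP 6.3 restores it.

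The effect per affected patient ranges from no change in the next dose to a reversal of the EWOC result at 400 mg q.d. (0.30 to 0.10, or 0.41 to 0.195). The reversals are always towards the higher dose. The first also needs DLTs in two successive cohorts.

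The conclusion rests on the literal reading of item 1, on the Table 7.1.1: 2 prior (which 7.1.1 allows to be updated), and on Part A only. It also depends on what withdrawal means in item 1, which does not say whether it is from treatment or from the trial. The documents do not show that any DLT was in fact excluded, and this point does not claim so. Part B was cancelled (SAP section 3), and the rationale for Amendment 4 (protocol 11.4) says primary-endpoint assessment is complete. What remains at stake is therefore the correctness of the final analysis set. Severity: should-fix.

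**What to change.** - Add to item 1 of protocol 3.3.4.1 the condition that the patient has not had a DLT, matching the other four items, and say whether withdrawal there means from treatment or from the trial.
- State in protocol 7.3.1.1 and SAP 6.3 that any treated patient with a DLT in cycle 1 belongs to the MTD evaluation set, whatever the later reason for leaving.
- Compare the treated-set and MTD-evaluation-set DLT counts for cycle 1 and confirm in the trial report that no cycle-1 DLT was excluded. If one was, rerun the MTD model with it included.

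The cost is one phrase and a clarification in 3.3.4.1, one sentence in each of the two set definitions, and one listing check. It needs no further patients, visits or procedures.
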